#### 5.1.2. Statistical methods

Student's unpaired t tests will be used to compare variables between groups. Correlation analyses will be performed using Pearson's correlation coefficient. Wilcoxon rank-sum test will be used to compare nonparametric data between groups. Fischer's exact test will be used to test differences in cross tables.

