## 2.2. Objectives

Hypotheses:

- By optimizing the use of sex specific reference values, we can improve the precision of the estimation of body fat volume using BIA measurements in trans gender males.

Aim:

- To assess body composition of trans gender males in hormonal therapy using BIA compared to DXA.
- To investigate whether binary reference values using BIA measurements in trans gender males in hormonal therapy is reliable – and thereby if BIA maybe a useful tool for assessing whether a trans gender man is suitable for mastectomy.

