### 3.4.2. Bioelectrical impedance analysis (BIA)

In each patient body composition is measured using the “male” and “female” setting of the Tanita MC-780 MA, respectively. BIA-measurements take less than 1 minute, are without any side effects, and a part of standard care in this patient group when assigned for weight loss therapy at the Department of Health Promotion.

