## 4. Data collection

Following the participants’ informed consent, data regarding age, sex, medication, onset of hormonal therapy, and blood samples (p-alanine transaminase, p-albumin, p-alkaline phosphatase, p-bilirubin, B-erythrocytes, B-hemoglobin, p-estradiol, p-follicle stimulating hormone, Hb(B)-hemoglobin A1c, p-cholesterol (LDL), B-leucocytes, B-erythrocyte volume (MCV), p-prolactin, p-sex hormone binding globulin, p-testosterone, p-free testosterone, p-thyroid screening, B-thrombocytes, p-lutropin will be collected from the participants’ EPJ. The information gathered is for use in the research project only.

The participants will be measured on the BIA scale twice and once with DXA and they will be asked questions about their habits concerning smoking and exercise. The center for Gender Identity regularly refers trans gender persons to the Department of Health Promotion for weight loss therapy. Patients at the Department of Health Promotion are routinely weighed on the Tanita MC-780 MA-scale. The blood samples collected in this study are routine samples and collected as a part of the participants treatment plan. DXA scans are not standard procedure in this patient group and is the only part of this project which is not part of the patient’s regular treatment plan.

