## 5. Data analysis

### 5.1. Statistical methods

#### 5.1.1. Sample size

In this study we aim to include 10 participants. It was not possible to conduct a sample size calculation based on the reference data on the Tanita MC-780 MA-scale, as Tanita will not share their data or information about their population. We have a vast experience with DXA scans in the clinic, and from this

experience we know that 10 persons will be enough to detect a difference in body composition in a pilot study.

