## 7. Study limitations

In this study we use a small cohort, and therefore we do not have the statistical foundation to be able to improve the sex specific reference values of BIA measurements, but we can use the data to assess body composition of trans gender males in hormonal therapy using BIA compared to DXA, and thereby assess whether BIA is a useful tool for assessing body composition in trans gender males. Furthermore, we aim to use these data for further hypothesis generation.

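### The only tests of difference named are for independent groups, yet the aim compares BIA with DXA in the same 10 people

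*Protocol*

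**What the plan says.** The first aim in Protocol section 2.2 is "To assess body composition of trans gender males in hormonal therapy using BIA compared to DXA". The second asks whether the binary BIA reference values are reliable in this population, with suitability for mastectomy as the intended use.

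The design is within person. Section 3.4.2: "In each patient body composition is measured using the" male and the female setting of the same device. Section 4: "The participants will be measured on the BIA scale twice and once with DXA". Section 3.2 defines one population and no comparison group.

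For the analysis, section 5.1.2 states that "unpaired t tests will be used to compare variables between groups", that "Wilcoxon rank-sum test will be used to compare nonparametric data between groups" and that "Correlation analyses will be performed using Pearson's correlation coefficient". It adds an exact test for cross tables. No paired test and no agreement analysis appears anywhere in the protocol.

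Section 5.1.1 asserts that "10 persons will be enough to detect a difference in body composition in a pilot study". Section 7 says the data will be used to compare BIA with DXA and "thereby assess whether BIA is a useful tool for assessing body composition in trans gender males".

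**The concern.** The three tests of difference in section 5.1.2 all assume that the values compared come from different people. In this study the BIA-male, BIA-female and DXA values come from the same people. The section does not say which test serves BIA against DXA, so it can be read in two ways.

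1. The unpaired t or rank-sum test is applied to BIA against DXA. The test then ignores the within-person correlation and leaves the spread between people in the error term.
2. The word groups refers to side subgroups, for example by smoking. The main comparison then has only Pearson's correlation. That coefficient is unchanged when a constant is added to every BIA value, so it cannot reveal a constant offset. A constant offset is the kind of error the protocol reports in section 2.1.2 from the BIA-MRI study it cites.

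Neither reading gives a fitting analysis of BIA error. The first pushes results towards non-significance, and in a method comparison a non-significant result is easily taken for agreement. A high correlation invites the same mistake. The protocol intends to draw a conclusion about the usefulness of BIA from these results.

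**Working it through.** **Inputs.** n = 10 (section 5.1.1). Significance level 0.05 (section 5.1.3); two-sided is assumed because the protocol does not say. The protocol gives no effect size, SD, power or BIA-DXA correlation, so there is no sample-size figure to reproduce. Results are in units of the between-person SD. The correlation r, equal SDs for the two methods, and normality are assumptions.

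**Standard error.** The true variance of the mean within-person difference is 2(1 − r)SD²/n. The unpaired test works with 2SD²/n. Its standard error is therefore too large by a factor 1/√(1 − r): 1.4 at r = 0.5, 1.8 at 0.7 and 3.2 at 0.9.

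**Observed mean difference needed for p < 0.05.**
- Unpaired, 18 df: 2.101 × √(2/10) = 0.94 SD, whatever r is.
- Paired, 9 df: 2.262 × √(2(1 − r)/10) = 0.72 SD at r = 0.5, 0.55 SD at 0.7 and 0.32 SD at 0.9.
- Break-even: r = 1 − (2.101/2.262)² = 0.14. Above this the paired test needs the smaller difference.

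**Power, unpaired against paired t test** (unpaired by simulation of correlated normal pairs, paired from the noncentral t distribution):

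| True mean difference | r = 0.5 | r = 0.7 | r = 0.9 |
|---|---|---|---|
| 0.5 SD | 12% v 29% | 8% v 45% | 4% v 88% |
| 0.75 SD | 32% v 56% | 29% v 78% | 26% v >99% |
| 1.0 SD | 59% v 80% | 61% v 95% | 64% v 100% |

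At a true difference of 0.94 SD the unpaired test has 52% to 55% power over these values of r, so below roughly that size it misses more often than it finds. At 1.5 SD it detects 94%, 97% and 99%.

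**Type I error of the unpaired test on paired data** (nominal 5%): about 1% at r = 0.5, 0.2% at 0.7 and below 0.01% at 0.9.

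**Rank tests.** At 0.75 SD, rank-sum against signed-rank power is 26% v 76% at r = 0.7 and 24% v 99% at r = 0.9.

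**The one BIA error in the protocol.** Section 2.1.2 cites an overestimate of fat-free mass by 12.4 kg (SD 6.2) against MRI in cancer patients, which is a weak analogy. The unpaired test would detect a mean error of that size more often than not unless the between-person SD exceeded about 12.4/0.94 = 13.2 kg. If 6.2 is the SD of the differences, which the text does not say, the limits of agreement are 12.4 ± 1.96 × 6.2 = 0.2 to 24.6 kg. On that assumption, a test of the mean alone says little about the error in one person.

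**The case against.** The strongest objection is that the protocol never assigns the unpaired tests to BIA against DXA. Smoking and exercise habits are collected and cross tables are planned, so side subgroups are a plausible meaning. The unpaired tests would then be correct where used, the 0.94 SD figure would not apply, and the gap could be filled in a separate analysis plan. The ambiguity is real. It does not rescue the section, because the aim would then rest on a correlation that cannot show an offset. Nor is the protocol silent on method: it fixes unpaired tests, and a later plan using paired ones would depart from it.

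A second objection is that 0.94 SD mostly reflects n = 10. At r = 0 the paired threshold is 1.01 SD, slightly worse. That is correct. The loss is the gap between the two tests, and it depends on r, which must be assumed. An r above 0.14 is nevertheless a mild assumption for two methods measuring the same quantity in the same person.

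Third, without a between-person SD for fat mass or fat percentage, the loss cannot be put in kilograms or percentage points. This stands.

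Fourth, this is a small pilot that states its limits, and the data as collected keep the pairing. This also stands: nothing is lost if the analysis is corrected before it is run.

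Finally, a non-significant paired test would not prove agreement either. That is right, and it is why the fix asks for intervals and limits of agreement and not only for a different test.

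**Conclusion.** The concern holds: the named methods do not fit the aim. The estimated mean BIA-DXA difference is the same under either analysis; what is wrong is its test and, under the second reading, the absence of any analysis of error. Under the first reading, mean differences below about 0.94 between-person SD would be missed more often than not, while differences of 1.5 SD would still be found at least 94% of the time. The claim in section 5.1.1 that 10 people suffice would then hold only for differences near one between-person SD or more. The 0.94 SD threshold rests on two-sided testing and equal SDs; the power figures also rest on normality and, for the comparison with a paired test, on the assumed r. The mismatch itself rests on no assumption, since it follows from sections 2.2, 3.2, 3.4.2, 4 and 5.1.2. It should be corrected before analysis because it affects the central comparison of the study.

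**What to change.** Replace the relevant part of section 5.1.2 with wording to this effect:

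- BIA and DXA are compared within participants.
- For BIA-male minus DXA, BIA-female minus DXA and BIA-male minus BIA-female, the mean difference is reported with its 95% confidence interval and a paired t test. The Wilcoxon signed-rank test is given alongside as a supporting check. Normality can hardly be judged from 10 differences, so the choice of test should not depend on it.
- For the two BIA-DXA comparisons, Bland-Altman limits of agreement are reported with 95% confidence intervals.
- Pearson's correlation is descriptive and is not taken as evidence of agreement.
- Unpaired t and rank-sum tests are used only for separate subgroups of participants.

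With n = 10 each limit of agreement has a 95% confidence interval of about ± 2.262 × √(1/10 + 1.96²/(2 × 9)) = ± 1.27 SD of the differences, so the limits should be labelled as pilot estimates. The cost is one paragraph of wording, with no new data, participants or procedures.

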#### 5.1.3. Statistical significance

We use a statistical significance level of  $\alpha < 0,05$ .

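### The aims need within-person agreement between BIA and DXA, but the analyses named in the protocol cannot measure it

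*Protocol*

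**What the plan says.** Section 2.2 (Objectives) gives two aims. The first is a method comparison: "To assess body composition of trans gender males in hormonal therapy using BIA compared to DXA". The second is "To investigate whether binary reference values using BIA measurements in trans gender males in hormonal therapy is reliable", and from that whether BIA may be a "useful tool for assessing whether a trans gender man is suitable for mastectomy". Section 7 (Study limitations) concedes that the cohort is too small to improve the reference values, but still says the data can be used to "assess whether BIA is a useful tool for assessing body composition in trans gender males".

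The design is one cohort of trans gender males in hormonal therapy (section 3.2), planned at 10 participants (section 5.1.1). Section 4 says: "The participants will be measured on the BIA scale twice and once with DXA". Section 3.4.2 explains the two BIA readings: one uses the device's male setting and one the female setting, in every participant.

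Section 5.1.2 names four methods: the unpaired t test and the Wilcoxon rank-sum test for comparisons between groups, Fisher's exact test for cross tables, and Pearson's coefficient ("Correlation analyses will be performed using Pearson"). Section 5.1.3 sets the significance level at 0.05. The groups are not defined, and section 5.1.2 does not say which variables each method is for. No within-person difference, limits of agreement or acceptable BIA–DXA error is named.

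**The concern.** The aims do not use the word agreement. But whether a reading is reliable against a reference, for a decision about one person, is a question of individual-level agreement. It needs two quantities for each BIA setting: the average error, and how widely individual errors scatter around that average.

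The listed methods fall short in three ways.

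1. Pearson's r measures linear association. Adding a constant to every BIA reading leaves it unchanged, so it cannot tell an unbiased setting from one with a fixed bias.
2. A non-significant difference in 10 people is not evidence of agreement.
3. No listed method estimates the person-to-person spread of BIA minus DXA.

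The two group-comparison tests also assume independent groups, whereas here the same people are measured by every method.

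At stake is the study's main conclusion. A significant r together with no significant mean difference could be reported as support for BIA while individual readings differ from DXA by several percentage points of body fat. DXA is also the only procedure outside routine care (section 4), and it is done for this comparison.

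**Working it through.** **Inputs from the protocol.** n = 10 (section 5.1.1); significance level 0.05 (section 5.1.3), taken as two-sided because sidedness is not stated; paired data (sections 3.4.2 and 4). The sample size has no effect size, SD or power behind it, so there is no stated figure to reproduce.

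**Assumptions.** The protocol gives no SD for fat percentage. The model is DXA ~ N(33, SD) and BIA = DXA − bias + error, with error ~ N(0, err), in fat-% points. SD is the between-person SD. There were 40,000 simulated samples of 10 people per setting.

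**1. Constant bias and r.** For any constant b, corr(DXA, BIA − b) = corr(DXA, BIA). At SD 7 and err 3 the mean r is 0.91 whether the bias is 0 or 7 points. On the same samples the largest change in r was 7 × 10⁻¹⁶, which is rounding error.

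**2. No mean bias, wide individual spread.** The true limits of agreement are ±1.96 × err: ±5.9 points for err 3 and ±7.8 for err 4. Share of samples in which r is significant and a *paired* test is non-significant:

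| err | SD 4 | SD 7 | SD 10 |
|---|---|---|---|
| 3 | 82% | 94% | 95% |
| 4 | 65% | 91% | 94–95% |

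The paired test is correct here, because there is no mean bias to find. The point is that this pair of results says nothing about a spread of ±6 to ±8 points. Pairing the test does not cure that.

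**3. Moderate bias with the planned unpaired test (err 3).** Share of samples in which r is significant and the difference is non-significant:

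| Bias | SD 4 | SD 5 | SD 6 | SD 7 | SD 8 | SD 10 |
|---|---|---|---|---|---|---|
| 5 | 25% | 48% | 69% | 83% | 91% | 97% |
| 7 | 2% | 9% | 23% | 42% | 61% | 84% |

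The reason shows in the standard errors at SD 7, err 3. Unpaired: √[(49 + 49 + 9)/10] = 3.27, so a 5-point bias gives t ≈ 5/3.27 = 1.5. Paired: 3/√10 = 0.95, so t ≈ 5/0.95 = 5.3. With a paired test the bias-5 shares fall to about 0.3% at err 3, and to about 3–6% at err 4. This part of the problem therefore comes almost wholly from ignoring the pairing.

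**4. The protocol's own example.** Section 2.1.2 cites a comparison of the same BIA device with MRI: mean overestimate of fat-free mass 12.4 kg, SD 6.2, error described as constant and correctable. If that SD is the SD of the differences, which the text suggests but does not spell out, individual errors run over 12.4 ± 1.96 × 6.2, about 0.2 to 24.6 kg. The unit, reference method and population differ from this study, so this only illustrates that a mean can hide the spread.

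**5. What an agreement analysis could deliver at n = 10.** With s the SD of the differences:

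- 95% CI half-width for the bias: 2.262/√10 = 0.72 s.
- 95% CI half-width for each limit: 2.262 × √(1/10 + 1.96²/18) = 1.27 s.

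For s = 3 points these are ±2.1 and ±3.8 points.

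**The case against.** The strongest case against has four parts.

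- **An analysis plan may exist.** Limits of agreement and difference plots are details a SAP often holds, and section 5.1.2 does not call its list complete. However, the section is not silent: it names methods, and the group comparisons it names do not fit the paired design. A SAP that follows it inherits the problem, and one that departs from it contradicts the protocol.
- **No faulty decision rule is stated.** This stands. The protocol nowhere says that a significant r or p ≥ 0.05 will count as reliable, and some methods may be meant for the hormone, blood, smoking or exercise data in section 4. The percentages above describe a risk of misreading, not a planned error. Even so, no other named method supplies the missing quantity.
- **It is a pilot.** Section 3.1 calls it one, and section 7 admits the small cohort and speaks of hypothesis generation. This limits what any analysis can show, but does not justify estimating a different quantity from the one the aims need.
- **A comparison of means is not worthless.** This also stands. It gives a point estimate of average bias, can rank the two settings on average, and would usually flag a gross bias.

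The unpaired tests and the missing agreement measure are also separable defects. Step 3 concerns mainly the first, step 2 only the second.

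**Conclusion.** The concern holds. As written, section 5.1.2 cannot answer the second aim, because none of its methods estimates how far one person's BIA reading may lie from DXA, and Pearson's r does not register a fixed bias. Under zero bias and true limits of ±5.9 to ±7.8 points, the potentially reassuring combination of a significant r and a non-significant paired test appears in 65% to 95% of samples of 10. With a 5-point bias and the planned unpaired test, the corresponding combination appears in 25% to 97%.

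These percentages depend on assumed SDs, error SDs and biases, and on normal distributions. The invariance of r and the absence of any measure of individual spread do not. The point should be settled before the data are analysed.

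**What to change.** Rewrite section 5.1.2 so that the primary analysis, separately for each BIA setting, is the within-person difference BIA minus DXA. Name the variable. Body-fat percentage is the one section 2.1.5 links to surgery, while the hypothesis in section 2.2 refers to fat volume, so the investigators should state which is primary. Then:

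- report the mean bias with its 95% CI;
- report 95% limits of agreement with CIs;
- plot differences against means to look for proportional bias;
- compare the male and female settings by the within-person difference in absolute error against DXA;
- have the investigators state, before data collection, the size of error they would accept, and judge reliability against it;
- keep Pearson's r as descriptive only, and say which variables and groups the remaining tests are for.

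The cost is protocol wording and a short analysis of measurements already planned, with no extra visits or scans. The drawback is that the intervals at n = 10 will be wide (step 5). They should be reported openly and the conclusion limited to match.

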#### 5.1.3. Statistical significance

We use a statistical significance level of  $\alpha < 0,05$ .

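### The protocol promises a verdict that BIA is reliable or useful, but the only criterion it fixes is p<0.05 on tests that cannot show agreement

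*Protocol*

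**What the plan says.** The second aim in Protocol 2.2 is: "To investigate whether binary reference values using BIA measurements in trans gender males in hormonal therapy is reliable". It goes on to ask whether BIA may help in judging suitability for mastectomy. Section 7 concedes that the cohort is too small to improve the reference values but keeps the verdict: the data are to be used to compare BIA with DXA, "and thereby assess whether BIA is a useful tool for assessing body composition in trans gender males".

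The statistical section offers this towards that verdict:

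- 5.1.1: "In this study we aim to include 10 participants", because from clinical "experience we know that 10 persons will be enough to detect a difference in body composition in a pilot study".
- 5.1.2: "Student's unpaired t tests will be used to compare variables between groups", rank-sum and Fisher tests, and "Correlation analyses will be performed using Pearson's correlation coefficient".
- 5.1.3: "We use a statistical significance level of" 0.05.

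On the data, section 4 says: "The participants will be measured on the BIA scale twice and once with DXA". Section 3.4.2 explains that the two BIA readings use the male and the female setting. Neither setting is named as the one the verdict concerns.

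**The concern.** The aim is a statement about agreement: do BIA and DXA give nearly the same answer in the same person? The tests and the sample-size argument are about finding differences. A difference test can show that two methods disagree on average. When it fails to do so, that may mean the methods agree or only that the study is small. Pearson's r measures whether readings rise and fall together, and adding a constant error to every BIA reading leaves r unchanged.

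The plan therefore contains no result that could properly support the word reliable or useful. Two wrong routes to it stay open: a p-value above 0.05 on a difference, or one below 0.05 on a correlation. With two settings measured and none designated, the better-looking one could be put forward after the data are seen. Section 8.3 says the findings may contribute to the treatment protocol on weight loss and referral for surgery, so an unsupported favourable verdict could have consequences.

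**Working it through.** **The plan's own figure.** N=10 cannot be reproduced, because 5.1.1 gives no expected difference, SD or power. The checks below take n=10 and alpha 0.05; two-sided is assumed, since the protocol does not say.

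**1. Paired t test (the more favourable case).** With d the true bias in SDs of the BIA-DXA differences, the noncentrality is d√10, on 9 df, with critical t 2.262.

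| True bias d | Noncentrality | Power | Missed |
|---|---|---|---|
| 0.5 | 1.58 | 0.293 | 71% |
| 0.7 | 2.21 | 0.506 | 49% |
| 1.0 | 3.16 | 0.803 | 20% |

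**2. The planned unpaired test.** It uses between-person spread, which has nothing to do with agreement. Assumptions, none from the protocol: SD of DXA body fat 7 points and SD of differences 3.5 points, independent of the DXA value.

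- Variance of BIA readings: 7² + 3.5² = 61.25.
- Unpaired standard error: √((49 + 61.25)/10) = 3.32. With t(18) = 2.101, significance needs an observed difference of about 7.0 points.
- Paired standard error: 3.5/√10 = 1.11. With t(9) = 2.262, significance needs about 2.5 points.

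In simulation under these assumptions, a true bias of 4 points is non-significant in about 94% of unpaired analyses. With between-person SD 6 to 8, SD of differences 3 to 4, and the bias set equal to 1.0 SD of the differences, the unpaired test is non-significant in 87% to 99% of studies, against 20% for the paired test.

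**3. Pearson's r.** At n=10 the critical value is 2.306/√(8 + 2.306²) = 0.63. With between-person SD 6 to 8, SD of differences 3 to 4 and biases of 3 to 5 points, r is significant in 92% to 99.7% of simulated studies despite the bias.

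**4. Precision at n=10.**

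- 95% CI half-width for the mean difference: 2.262/√10 = 0.72 SD.
- 95% CI half-width for each limit of agreement: 2.262 × √(1/10 + 1.96²/18) = 1.27 SD.

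The only SD in the protocol for this device is 6.2 kg. It comes from a cited comparison of fat-free mass with MRI in 18 colorectal cancer patients (2.1.2), so it is an assumption here. With it, the half-widths are 0.715 × 6.2 = 4.4 kg and 1.27 × 6.2 = 7.9 kg.

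**5. Two settings.** If the settings were off by equal and opposite amounts with the same person-level error, a paired test would leave at least one non-significant in 98% of studies at ±0.5 SD, 84% at ±0.7 SD and 39% at ±1.0 SD. This shows why the setting matters. The symmetry is assumed.

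**The case against.** A reader might infer that BIA would be called reliable because a difference was not significant, and that one setting passing would be enough. The protocol says neither. It states an alpha level and aims, and no rule connects a test result to the verdict. Section 5.1.1 expects to detect a difference, and the background argues that the equations may work poorly in this population. Measuring both settings is the design, since the aim concerns binary reference values. So the fair wording is that non-significance could be misread as agreement.

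It would also go too far to say that an error that matters would usually be missed. The documents do not say which error matters. The cited study reports a mean of 12.4 kg with SD 6.2 kg, that is 12.4/6.2 = 2.0 SD; a paired test with 10 people detects a bias of that size with more than 99.9% power. The 98% figure for two settings depends on an assumed symmetric scenario and should not be the headline.

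Two further points deserve weight. First, an analysis plan not shown may hold an acceptable error or a primary comparison, so their absence alone is no finding. What remains is a mismatch within the protocol itself: a promised agreement verdict beside difference tests, correlation and a sample size argued from detecting a difference. Second, this is a 10-person pilot that admits its small cohort and undertakes to publish inconclusive results (8.6). That lowers the severity. It does not remove the point, because section 7 keeps the usefulness verdict and offers hypothesis generation as an additional purpose.

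**Conclusion.** The point holds in this limited form. The protocol sets out to conclude whether BIA is reliable or useful, and what it fixes for that purpose cannot support the conclusion. With 10 people, non-significance is weak evidence: even a paired test misses 71% of true biases of 0.5 SD of the differences and 20% of those of 1.0 SD. The unpaired test misses more whenever BIA and DXA readings are positively correlated, as two measures of the same quantity should be. A significant correlation is likely whether or not BIA is biased.

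The paired figures rest only on n=10, a two-sided 0.05 level and normally distributed differences. The unpaired and correlation figures rest on assumed body-fat SDs, and the kilogram figures on an SD borrowed from another population and reference method. Making the tests paired would help but would not cure the problem, since a p-value still does not say whether the error is small enough. This is worth correcting before the first measurement; for a pilot of this size it is not fatal to the study.

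**What to change.** In 5.1.3 and 7, state that significance tests and Pearson's r are not the basis for calling BIA reliable or useful. Then:

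- Name one outcome, for example body fat percentage. Report the paired BIA-DXA mean difference and limits of agreement, with 95% CIs, for both the male and the female setting.
- Before the first measurement, have the department fix the largest BIA-DXA error it would accept. State which setting the verdict applies to, or that both are reported and neither is selected after the data are seen.
- Call BIA useful only if the CI of the bias and the limits of agreement lie inside that error. Otherwise report the result as not shown, whatever the p-value.

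Alternatively, limit the pilot to estimating bias and limits of agreement, and drop the verdict from 2.2 and 7.

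The cost is a few sentences. The downside is that 10 people will probably give an inconclusive result. Even for the mean bias alone, two one-sided tests at 0.05 with no true bias have about 80% power only if the acceptable error is about 1.0 SD of the differences; power is about 43% at 0.75 SD and 7% at 0.5 SD, where about 36 people would be needed for 80%. Limits of agreement at ±1.96 SD ask for more still.
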